### 12.12. Other Data

Protocol deviations will be listed and summarized. Surgical information will be summarized. Individual components of the Functional Comorbidity Index (FCI) questionnaire may be summarized.

### 13. Comparability to Aequalis Dataset

Demographics and baseline characteristics for subjects in the Aequalis dataset and subjects with the investigational system will be compared by t-tests for continuous factors and chi square tests for categorical factors; non-parametric or exact tests may be used when appropriate. These characteristics will include age, gender, diagnosis, and baseline adjusted Constant score. No imputations will be done for these comparisons. Additional baseline measures may be considered if sufficient non-missing values are available. A propensity score analysis may also be performed on the subjects with complete 24 month status/data available if differences in the populations are observed. The propensity score analysis will incorporate data from Aequalis dataset used to derive the performance goal and subjects enrolled in the current investigation. If significant differences are found between groups, the impact of relevant factor(s) on the primary endpoint success rate will be assessed by logistic regression.

### 13.1. Aequalis Data

A subset of data from the Tornier Aequalis Post-Market Outcomes Study was used to develop the performance goal for the primary endpoint hypothesis test of the current investigation. A total of 191 subjects from the post-market study had an indication similar to that of the current investigation and had endpoint status at 24 months determined. Their available data will be used in the comparison to the current investigation.

# 13.2. Propensity Score Analysis

A propensity score adjusted analysis will be performed as a supplemental analysis to the primary analysis if any of the standardized mean difference between the two groups for the list of confounders differs by more than 10% (see below more specifics). This section provides additional details for that analysis.

Propensity score based methods may be used to account for significant imbalances in baseline confounding characteristics between the current investigation and Aequalis. The final analysis will be a propensity score adjusted analysis on the primary endpoint by using a logistic model to model probability of success adjusted by the final propensity score. 95% confidence bounds will be calculated for the difference in probability of success between the current investigation and Aequelis (Aequalis – current investigation). If the upper bound for the mean difference excludes the non-inferiority margin of 10%, non-inferiority has been met for the propensity adjusted analysis.

The current investigations study data will be sent from the sponsor to the independent statistician in the format of SAS datasets. The sponsor does not have capability to access or analyze data in this format.

These analyses will be performed by two statisticians, both independent statisticians (i.e. not sponsor employees):

- The propensity score statistician (PS statistician) will receive blinded data from the independent statistician and will construct the propensity scores and have no access to the outcomes of the trial to prevent bias. The PS statistician will remain blinded to the outcomes.
- The independent statistician is unblinded and will prepare a blinded SAS dataset with the specified covariates and study ID with no outcome data and send to the PS statistician. The unblinded statistician will complete all other summaries for the report and incorporate the final propensity scores received from the PS statistician into the primary endpoint comparison. The PS statistician will not complete any analysis that involves the study endpoints.

The propensity score is the likelihood that a patient would be assigned to the current investigation given the profile of his/her baseline characteristics. The propensity score will be derived from a propensity score model developed using a multivariate logistic regression with the study (current investigation vs Aequalis data) as the response variable and the following potential baseline confounders as predictors:

- Gender
- Age

- Baseline adjusted constant score
- Diagnosis
  - Avascular Necrosis
  - Primary Glenohumeral Osteoarthritis
  - o Post-Traumatic Arthritis
- Body Mass Index

Simple imputation will be done to any missing baseline data points used in the propensity score model. For continuous covariates with missing information, the mean population value for the study (i.e., Aequalis data, current investigation) will be used. For categorical covariates with missing data, the level with the highest proportion of patients for the study will be assigned.

#### Building the Propensity Model (performed by blinded propensity score statistician)

The propensity score is a probability (of being in the current investigation) and will range from 0 to 1, such that patients with a higher score are more likely to have been part of the current investigation than those with lower propensity scores.

The fit of the propensity score model is critical. All confounders will be entered into the logistic regression model and kept in the model regardless of statistical significance due to the small number of confounders. One logistic model will use the confounders only as main effects. The second logistic model will use the main effects, the quadratic terms for age and baseline adjusted constant score and all 2-way interaction terms.

# Checking for improvement in confounder balance between the original (unadjusted) comparison and the propensity score adjusted comparison

The imbalance in confounders will be assessed in the original study groups. Per Austin (2006) the standardized mean difference will be used and the sum of the absolute value of the standardized differences over all confounders will serve as the overall measure of covariate balance in the original group.

Per Austin (2008), the equivalent to the absolute value of the standardized mean difference when covariate adjustment is used is the absolute value of the weighted conditional standardized difference. This value will be summed over all confounders and compared to the value in the original group for the two proposed propensity score models. The propensity score model with the lowest sum of the absolute values of the weighted conditional standardized difference will be selected. It is expected that this sum will be less than that calculated for the original group and if so represents the improvement in covariate balance due the adjustment by the propensity score in the primary endpoint comparison.

However, if any of the individual absolute values of the weighted conditional standardized differences are greater than 10% (0.10) with the selected propensity model, we will then follow the "rule of thumb" suggestion by Crump et al. 2009, and use only propensity scores in the range [0.1, 0.9] to see if that resolves the issue. If after limiting the subjects to that range, there are no mean differences greater than 10% and the summed value has decreased further, only those subjects with propensity scores in that range will be used in the comparison. If it does not, we will limit the sample to the region of common support and if that resolves the issue, the

patients in the region of common support will be used. If it does not, the full sample size in both groups will be used.

Using the selected propensity score model, the extent of overlap between the study groups will be compared using box plots. Additionally, the propensity scores for all subjects (current investigation and Aequalis, combined) will be stratified into quintiles (each containing as close to 20% of the population as possible) and the proportion of Pyrocarbon and Aequalis subjects in each quintile will be compared to see if there is sufficient overlap in the scores. Sufficient overlap will be defined as at least 10 subjects of each group (current investigation vs. Aequalis) within a stratum. If sufficient overlap is not found, we will limit the primary endpoint comparison using either "rule of thumb" suggestion by Crump et al. 2009, [0.1, 0.9] or the region of common support.

Ultimately, the largest sample of patients providing improved balance in confounders with acceptable overlap will be used in the analysis. As a sensitivity analysis, the propensity score adjusted primary endpoint comparison will be made in the remaining two patient groups as appropriate, i.e. sufficient overlap exists and improvement in confounder balance was achieved.

Version	Date	Changes
1.0	20JUL2015	Initial version.
2.0	17AUG2015	Updated to include 150 total enrollments Clarified difference between enrolled and implant
		attempts
3.0	18AUG2015	Clarified unsuccessful implant attempts are primary endpoint failures
4.0	11SEP2015	Updated to match updated protocol including updated sample size calculation, data collection, follow-up windows, adding revision rate and radiographic summaries comparing to Aequalis
5.0	18AUG2017	Updated and expanded propensity score adjusted analysis.
6.0	07JAN2019	Updated to add BMI to propensity score model. Added a revision rate for secondary endpoint.

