### **10. Sample Size Considerations**

Statistical considerations for powering the primary endpoint include the following:

- 80% power with a one-sided 0.025 level of significance
- Non-inferiority test of one proportion
- 10% non-inferiority margin, and performance goal of 85%
- Assumed investigational system success rate of 85%
- Attrition rate of 15%

The sample size for this endpoint was calculated using SAS (Version 9.3) under a one-sided z-test of a binomial proportion. The minimum required sample size is estimated using the above list of statistical considerations. The resultant sample size under these assumptions is 133 subjects. With 15% attrition, 157 total subjects with an attempted implant are needed. Up to 190 subjects may be enrolled to account for pre and intra-operative screen failures. Enrollment will stop once 157 subjects have had an implant attempt.

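### SAP 13.2 gives two sample-selection rules for the propensity analysis that can conflict, and its last fallback keeps a score-only outcome model after the SAP's own balance check has failed

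*SAP*

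**What the plan says.** SAP 13.2 (Propensity Score Analysis) describes a comparison with the Aequalis dataset that supplements the primary analysis. It runs if any listed confounder has a standardized difference above 10%. The outcome is analysed "by using a logistic model to model probability of success adjusted by the final propensity score"; no other adjustment term is named. Non-inferiority counts as met for this analysis if the upper bound for Aequalis minus current investigation excludes 10 points.

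The sub-section on checking confounder balance then gives two sets of instructions on who enters the comparison.

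- **Balance rule (third paragraph).** If any weighted conditional standardized difference exceeds 0.10 under the selected score model, subjects are restricted to scores from 0.1 to 0.9. That sample is kept if no difference exceeds 0.10 and the summed difference has fallen further. Otherwise the region of common support is tried. If that also fails: "If it does not, the full sample size in both groups will be used".
- **Overlap and closing rule (last two paragraphs).** The scores are cut into quintiles, and each must hold at least 10 subjects of each group. "If sufficient overlap is not found, we will limit the primary endpoint comparison using either" the 0.1 to 0.9 range or common support. Then: "Ultimately, the largest sample of patients providing improved balance in confounders with acceptable overlap will be used in the analysis". A sensitivity analysis repeats the comparison in the other two samples where overlap is sufficient and balance improved.

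**The concern.** The two rules use different criteria. The balance rule requires every difference to be at or below 0.10 and has no overlap condition. The closing rule requires overlap but only better balance than before. Neither is said to take precedence, and the choice between the two trims for poor overlap has no order. Two analysts who both follow the SAP could therefore report different samples as the main adjusted result.

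The last fallback raises a second problem. The differences being checked are already conditional on the score. Reaching the fallback means that adjusting for the score has left at least one covariate outside the SAP's own limit. The outcome model then relies on that score alone, with no added covariate, no caveat and no upper limit on the residual. It can still return a statement that non-inferiority was met. What is at stake is the credibility of the supplemental comparison with the historical data.

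**Working it through.** **1. The plan's own figures.** SAP 10 gives "80% power with a one-sided 0.025 level of significance", "10% non-inferiority margin, and performance goal of 85" (per cent), "Assumed investigational system success rate of 85" (per cent) and "Attrition rate of 15" (per cent). With a one-sample z-test and null rate 0.85 − 0.10 = 0.75:

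n = [(1.96 × √(0.75 × 0.25) + 0.8416 × √(0.85 × 0.15)) / 0.10]² = 132.07, so 133. Then 133 / 0.85 = 156.5, so 157.

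Both reproduce. SAP 13.1 gives 191 Aequalis subjects. The documents state no power or bias figure for the propensity analysis.

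**2. The two rules side by side.**

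| Situation | Balance rule | Overlap and closing rule |
|---|---|---|
| Full sample: balance improved, all quintiles have at least 10 per group, one difference 0.12. Range 0.1–0.9: all differences at most 0.10, lower sum | Range 0.1–0.9 | Full sample (the largest that qualifies) |
| Both trims leave a difference above 0.10; one full-sample quintile has fewer than 10 of a group | Full sample | A restricted sample, by either trim |
| Both trims leave a difference above 0.10; no sample has both improved balance and acceptable overlap | Full sample | No answer |

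In the first row both instructions are explicit and cannot both be followed.

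**3. Will the analysis run?** With 133 and 191 subjects, the SE of a standardized difference is √(1/133 + 1/191) = 0.113. With no true group difference, one covariate exceeds 0.10 in absolute value with probability 2 × [1 − Φ(0.10/0.113)] = 0.38. For 5 to 6 independent covariates, the chance that at least one does so is 1 − 0.62⁵ to 1 − 0.62⁶, which is 0.91 to 0.94 with unrounded inputs. The trigger will very probably be met.

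**4. Size of a residual imbalance.** The shift in the success difference is approximately p(1 − p) × ln(OR per SD) × d, with p = 0.85, so p(1 − p) = 0.1275. The odds ratios are assumptions; the documents give none.

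- OR 1.25, d = 0.10: 0.1275 × 0.223 × 0.10 = 0.3 points.
- OR 2, d = 0.10: 0.1275 × 0.693 × 0.10 = 0.9 points.
- OR 1.25, d = 0.20: 0.6 points.
- OR 2, d = 0.20: 1.8 points.

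For context, at 85% in both groups the unadjusted 95% half-width is 1.96 × √(0.1275 × (1/133 + 1/191)) = 7.9 points, which leaves 10 − 7.9 = 2.1 points. At the margin (85% against 75%) the SE is √(0.1275/191 + 0.1875/133) = 0.0456. If the shift favours the device, the one-sided error of this supplemental test rises from 0.025 to 0.029 (0.3 points) or 0.058 (1.8 points). If it runs against the device, the error falls.

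**5. How often the fallback is reached.** The documents do not allow this to be derived. An illustrative simulation used five assumed patterns of group difference, 300 replicates each. The fallback occurred in 86% to 98% of replicates when conditional differences were averaged in absolute value, and in 0.3% to 0.7% when averaged with sign. The SAP cites a methods paper for the measure but does not write out the formula.

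**The case against.** The strongest reply is that little depends on this. The analysis is supplemental, and trial success rests on the one-sample lower bound (SAP 8 and 12.5.1), which nothing in 13.2 can change. That stands.

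The SAP also has safeguards. The adjusted comparison is repeated in the other two samples, so often all three results would be seen. SAP 13 adds logistic regression on relevant factors if the groups differ significantly. The statistician who builds the scores is blinded to outcomes, and selection uses only covariates and scores. These help in part. The repeat analyses are conditional on overlap and improved balance, and they do not settle which result leads. The regression is triggered by significance and is separate from the propensity verdict.

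Part of the conflict can be read as sequence: balance first, overlap second. That explains trimming for overlap after a balance check. It does not resolve the first row of the table unless the closing sentence is taken as a mere summary, which is plausible but not stated. Returning to the full sample is also defensible in itself, because trimming costs subjects and changes the target population.

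A reader might infer that the fallback knowingly rests a verdict on confounding. The documents do not support that. A weighted conditional difference above 0.10 is what remains after score adjustment, not raw imbalance. It biases the result only if the covariate is prognostic, and in either direction. The documents give no prognostic strengths.

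**Conclusion.** The point holds as an inconsistency in the SAP with a modest possible effect. The two rules can select different samples from the same data. In the last fallback, a non-inferiority statement can follow from a score-only model after that score has failed the SAP's 0.10 check.

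At an assumed OR of 1.25 to 2 per SD, a residual of 0.10 to 0.20 in one covariate moves the success difference by about 0.3 to 1.8 points, or 3% to 18% of the 10-point margin. Larger residuals are not excluded by the SAP, and shifts from several covariates could add or cancel. These figures use a linear approximation at 85% success. It cannot be said from the documents how often the fallback would occur. The primary conclusion is untouched.

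**What to change.** Replace both rules with one order, applied by the outcome-blinded propensity score statistician:

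1. Take the full sample, then scores in 0.1 to 0.9, then common support. Stop at the first with every weighted conditional difference at or below 0.10 and at least 10 subjects per group in each quintile. For a trimmed sample, keep the existing condition that the summed difference has decreased.
2. If none qualifies, use the sample with the smallest summed difference among those meeting the overlap criterion. Add every covariate still above 0.10 to the outcome logistic model alongside the score.
3. If no sample meets the overlap criterion, report the estimate descriptively, without a non-inferiority statement.
4. Delete the unordered choice between trims and the separate closing rule on the largest sample. Keep the sensitivity analyses in the other samples.

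The cost is SAP wording. The covariates are already specified for the score model. At 85% success, about 0.15 × (133 + 191) = 49 failures would be available in the full sample, enough for one or two extra terms with a slight loss of precision.
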